8.2.7 PHASE II DOSE EXPANSION PERIOD STOPPING RULES

Further computations of the DLT rate will be performed during the Expansion Period in order to incorporate study stopping rules. During the Expansion Period, the DLT rate will be calculated as events occur. The DLT rate will be defined as the ratio of the total number of patients with a DLT at the MTD/RDE divided by the total number of patients enrolled at that dose level who are evaluable for DLT (for evalutability see Section 8.4.4).

If the DLT rate is $\geq 33\%$, a temporary study suspension of enrollment at the MTD/RDE will be required in order to perform a thorough and in-depth review of the available safety information to determine whether additional patients should be enrolled at that dose level. The SRC may decide to enroll 3 more patients at the MTD/RDE and review the DLT rate again once those patients become evaluable for DLT. Alternatively, if the SRC determines that there is a reasonable probability that the DLT rate will remain higher than 33% with further enrollment of patients at that dose level, then the SRC may decide to stop enrollment at the MTD/RDE and permit expansion of a dose level lower than the MTD/RDE. Enrollment at the new RDE will be subject to the same enrollment and stopping rules as expansion at the MTD/RDE.

In addition, any Grade 4 toxicity related to mRNA-2416 during the Expansion Period will require a temporary suspension of expansion and review by the SRC. A drug-related death at any time during the study would result in study pause and expedited notification to FDA per 21 CFR 312.32

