8.4 DOSE ESCALATION PROCEDURES

8.4.1 SAFETY REVIEW COMMITTEE (SRC)

A SRC composed of the study Medical Monitor, Sponsor representatives, and enrolling Principal Investigators (PIs) will hold teleconferences at the completion of each dose cohort in the Dose Escalation Period and during the Expansion Period, as needed, to review and assess all available safety data and the treatment status of all patients.

A written summary documenting the results, and recommendations of each review, including SRC consensus regarding recommended dose escalations or MTD/RDE, will be provided to the investigator(s) and maintained on file with the Sponsor. Additional personnel may participate in reviews as indicated.

Following a cohort review, the mRNA-2416 SRC may recommend proceeding with enrollment in the next dose cohort, enrolling additional patients in the current cohort, dropping back to a lower cohort, or not enrolling any additional patients. The dose escalation guidelines outlined in [Section 8.4.4](#), as well as the study stopping rules outlined in [Section 8.2.6](#), will be used as the basis for all SRC decisions.

While the SRC is expected to reach a consensus opinion regarding any premature discontinuation or significant modification of the study, the Sponsor may independently stop the study.

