8.4.2 DEFINITION OF DOSE-LIMITING TOXICITIES

A dose-limiting toxicity (DLT) is defined as an adverse event or abnormal laboratory value assessed as unrelated to disease, disease progression, inter-current illness, or concomitant medications and at least possibly related to the study therapy and that occurs within the first 28 days of study therapy. The investigator must notify the Sponsor immediately of any DLTs.

For patients in Arm A receiving mRNA-2416, the following toxicities will be considered a DLT:

- All Grade 3 AEs with the exception of the following:
 - Grade 3 thrombocytopenia lasting <7 days
 - Grade 3 neutropenia without fever or lasting <7 days
- Any Grade 4 or Grade 5 toxicity. Death due to disease progression is not considered a DLT.

For patients in Arm B receiving mRNA-2416 in combination with durvalumab, the following toxicities will be considered a DLT:

Adverse Event (AE)+C2:F16	DLT Criteria		
	Grade 2 Events	Grade 3 Events	Grade 4 events
Diarrhea/colitis	none	Events that do not resolve to Grade 1 or baseline within 14 d (whether or not it is immune-mediated)	DLT
Pneumonitis	Non-infectious pneumonitis that does not resolve to Grade ≤1 within 10 days	Non-infectious pneumonitis is a DLT	DLT
Hepatitis	none	Alanine aminotransferase (ALT) or aspartate aminotransferase (AST) >8×ULN or total bilirubin (TBL) >5×ULN OR events meeting Hy's Law (AST or ALT ≥3×ULN with concurrent increase in TBL ≥2×ULN without evidence of cholestasis or alternative explanations)	DLT
Rash	Any grade rash with bullous formation.	Rash not resolving to Grade 1 or baseline within 30d. Any rash with bullous formation.	DLT
Peripheral neuromotor syndromes such as Guillain-Barre or myasthenia gravis	Events not resolving to Grade 1 within 30d. Events with any signs of respiratory insufficiency or autonomic instability.	Events that do not resolve to Grade 1 within 30d. Events with any signs of respiratory insufficiency or autonomic instability.	DLT
Myocarditis	Events that do not resolve to Grade 1 within 3d OR a biopsy confirms immune-mediated myocarditis.	All Grade 3 myocarditis.	DLT
Myositis/polymyositis	Events that do not resolve to Grade 1 within 30d OR exhibit signs of respiratory insufficiency regardless of optimal medical management	Events that do not resolve to Grade 1 within 30d OR exhibit signs of respiratory insufficiency regardless of optimal medical management	DLT

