8.4.3 DEFINITION OF MTD

The MTDs will be defined as the highest dose of mRNA-2416 alone and in combination with durvalumab at which a DLT has been seen in less than 2 of 6 patients (<33%) during the first 28-days of study therapy.

If 2 or more adverse events that meet the definition of a DLT as defined in [Section 8.4.2](#), are observed beyond the first 28 days of study therapy within a dose escalation cohort, further enrollment may be held, pending safety analysis of the events by the SRC. These events will not affect the determination of the MTD but will be used in determining the appropriate RDE.

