8.4.4 DOSE ESCALATION PROCEDURE

In order to be evaluable for dose determination, a patient must have received $\geq 50\%$ of the planned mRNA-2416 dose and $\geq 75\%$ of the planned durvalumab dose (Arm B) for Cycle 1 and must either have been followed ≥ 28 days following the first dose or have experienced a DLT within 28 days of the first dose. Patients who are not evaluable for dose determination may be replaced.

Dose escalation determination will not occur until the third patient in a cohort has completed their first 28-day study therapy.

- If no patient (0 of 3) in a dose cohort experiences a DLT during the first 28 days, then the next dose cohort of 3 patients will be enrolled at the next dose level per [Table 1](#) following consensus of the SRC.
- If 1 of 3 patients in a dose cohort experiences a DLT, an additional 3 patients will be enrolled in that dose cohort.
 - Provided that no more than 1 of 6 patients in the expanded dose cohort experiences a DLT within 28 days of the first dose, then a dose cohort of 3 patients will be enrolled at the next dose level per [Table 1](#) following consensus of the SRC.
- If ≥ 2 patients in a dose cohort experience a DLT within 28 days of the first dose, that cohort will have exceeded the MTD. No additional patients will be dosed at that level, and 3 patients will be enrolled in the preceding dose cohort, unless 6 patients have already been treated at that dose level. Using the same criteria, lower dose cohorts will be explored as the MTD until ≤ 1 of 6 patients experiences a DLT.

In the event that ≥ 2 of the first 6 DLT-evaluable patients in the 1.0 mg cohort experience a DLT, then the next cohort will be dosed with 0.5 mg mRNA-2416.

In the event that ≥ 2 of the first 6 DLT-evaluable patients in the 8.0 mg cohort experience a DLT, an intermediate dose cohort may be opened at 6.0 mg mRNA-2416.

9 **SELECTION OF PATIENTS**

9.1 **INCLUSION CRITERIA**

All patients must meet all of the following inclusion criteria:

1. Males or females ≥ 18 years of age who have provided written informed consent prior to completing any study-specific procedure
2. Disease state and prior therapies:

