12.3 RELATIONSHIP TO STUDY DRUG

For each reported AE, the investigator must make an assessment of the relationship of the event to each study drug using the following scale:

- Not Related: An event that is not associated with study drug administration and is judged clearly due to causes other than the study drug.
- Related: An event that is or may be associated with study drug administration.

- The terms Possibly Related and Probably Related will not be used. Any event that is possibly or probably related to study drug should be recorded as Related by the Investigator.

In the event of death, the cause of death should be recorded as the AE and the relationship to study drug assessed as above. “Death” is an outcome and is NOT the AE. The only exception is “sudden death” when the cause is unknown.

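### In Arm B Expansion, a non-fatal Grade 4 event recorded as related to durvalumab but not to mRNA-2416 does not trigger the single-event Grade 4 rule in Protocol 8.2.7

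*Protocol*

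**What the plan says.** Protocol 8.2.7 governs Expansion in both arms and has three mandatory triggers.

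- **DLT rate.** For the MTD/RDE, "the DLT rate will be calculated as events occur". The denominator is every DLT-evaluable patient at that dose level. A rate of 33% or more suspends enrollment for an in-depth safety review.
- **Single Grade 4 event.** "any Grade 4 toxicity related to mRNA-2416 during the Expansion Period will require a temporary suspension of expansion and review by the SRC".
- **Death.** "A drug-related death at any time during the study would result in study pause".

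Three other sections bear on how these work.

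- Section 12.3 asks for a separate Related / Not Related call for each study drug. It leans toward Related: "Any event that is possibly or probably related to study drug should be recorded as Related by the Investigator". Not Related is kept for events judged clearly due to something else.
- Section 8.4.2 defines a DLT at regimen level, as an event "at least possibly related to the study therapy and that occurs within the first 28 days of study therapy".
- Section 8.4.1 has the SRC meet "during the Expansion Period, as needed, to review and assess all available safety data".

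**The concern.** The single-event rule names one drug in a section that also covers the combination arm. Because relatedness is recorded per drug, related to durvalumab only is a possible entry, and an event with that entry falls outside the rule. The neighbouring rules are wider: the death rule speaks of drug-related death, the DLT definition of study therapy, and the Grade 4 discontinuation rule in 10.5 of treatment-related events. The documents give no reason for the narrower wording here. The summary of changes for the amendment that added Arm B lists updates to DLT definition and evaluability but none to the stopping rules, and 8.4.1 still points to 8.2.6 for them. That suggests text carried over from the monotherapy design, but this is an inference.

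At stake is whether the committee that advises on further Arm B enrollment must look at such an event. Durvalumab alone is well known (more than 6000 patients, 6.3). This is the first-in-human study of mRNA-2416 (6.2), so the combination is new. Both drugs are given on Day 1 of each combination cycle, with at least a 30-minute gap (10.1), so one drug's effect is hard to separate from the other's. Section 6.2 reports 8/15 complete responses in mice on the combination against 1/15 in each single-agent control group. Those are activity data and show nothing about toxicity. They are a reason not to rest mandatory review on one attribution call.

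**Working it through.** **1. Does any other rule require SRC review of this event?**

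| Provision | Effect on a durvalumab-only, non-fatal Grade 4 event in Expansion |
|---|---|
| 8.2.7, Grade 4 rule | Not triggered; names mRNA-2416 only |
| 8.2.7, death rule | Not triggered; event is non-fatal |
| 8.2.7, DLT rate | Generally counted if within 28 days; review only at 33% or more |
| 8.4.3, late events | Two or more DLT-type events that "are observed beyond the first 28 days of study therapy within a dose escalation cohort, further enrollment may be held": optional, and escalation cohorts only |
| 8.4.1 | SRC calls as needed; Sponsor may stop the study |
| 10.5 and Appendix E | Act on the individual patient |
| 8.4.2, 12.2, 12.1.5 | Immediate DLT notice, 24-hour SAE reporting, AESI reporting; none requires SRC review |

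**2. The plan's own threshold.** 8.4.3 equates fewer than 2 of 6 with under 33%. 2/6 = 33.3%, which meets the 8.2.7 limit. The two sections agree.

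**3. Can one event reach 33% at the dose taken into Expansion?**

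Inputs: Escalation and Confirmation (run the same way, at least 3 patients, 8.2.4) each contribute 3 to 6 evaluable patients at that dose. This is an assumption. Each cohort is cleared with 0 of 3, or under the 8.4.4 condition "Provided that no more than 1 of 6 patients in the expanded dose cohort experiences a DLT within 28 days of the first dose".

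Formula, with d earlier DLT patients among n earlier evaluable patients: rate = (d + 1)/(n + 1) at the first Expansion patient.

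- 0/3 and 0/3: 1/7 = 14.3%
- 0/3 and 1/6: 2/10 = 20.0%
- 1/6 and 1/6: 3/13 = 23.1% (highest)
- 0/6 and 0/6: 1/13 = 7.7% (lowest)

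All are below 33%, so one event does not suffice.

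**4. Where one event would suffice.** 8.2.7 lets the SRC move expansion to a lower dose under the same rules, and Table 2 lists 2.0 mg plus durvalumab. With no earlier DLT, 1/(n + 1) reaches 33% only if n is at most 2: 1/1 = 100%, 1/2 = 50%, 1/3 = 33.3%, but 1/4 = 25%.

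**5. Total DLT patients needed for 33%, earlier ones included.**

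| Evaluable at the dose | Needed | Rate | One fewer |
|---|---|---|---|
| 7 (first Expansion patient, 6 earlier) | 3 | 42.9% | 28.6% |
| 13 (first Expansion patient, 12 earlier) | 5 | 38.5% | 30.8% |
| 21 (Stage 1 complete, 15 + 6) | 7 | 33.3% | 28.6% |
| 27 (Stage 1 complete, 15 + 12) | 9 | 33.3% | 29.6% |

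Under the mRNA-2416 rule, one event is enough.

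**6. After Day 28.** Combination dosing lasts 6 × 28 = 168 days. The DLT window covers 28, leaving 168 − 28 = 140 days (Cycles 2 to 6) in which no Expansion rule counts the event. This is calendar time for a patient who completes combination dosing, not a share of risk.

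**The case against.** The strongest reply is that 12.3 already does most of the work. An event that mRNA-2416 may have worsened may be associated with it, so it must be recorded as Related, and the existing rule then suspends expansion. A reader might infer that toxicity made worse by the combination escapes mandatory review. The documents do not support that: if 12.3 is applied as written, only events judged clearly not due to mRNA-2416 are left. What remains is a true durvalumab-only event, or a wrong attribution.

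The narrow trigger can also be defended as design. It attaches to the first-in-human agent, whose dose the SRC controls. Durvalumab is fixed at 1500 mg with no reductions allowed (10.4), has a large safety record, and has its own Grade 4 guidance in Appendix E.

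Nor does the event go unseen. DLTs must be notified to the Sponsor immediately, SAEs are reported within 24 hours, and the SRC itself includes the Medical Monitor, Sponsor representatives and enrolling investigators. What is missing is an obligation to review, not a route to the people who would do it.

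All of this stands and limits the point. It does not answer the textual gap, or the dependence of mandatory review on one attribution judgment between two drugs given the same day.

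**Conclusion.** The point holds as a narrow gap of small size. A non-fatal Grade 4 event recorded as related to durvalumab and Not Related to mRNA-2416 does not trigger the single-event rule. Within 28 days it generally counts only toward the DLT rate, and after Day 28 toward no Expansion rule.

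A reader might go further and conclude that one such event can never force a review. That is not supported: at a lower dose level with at most two earlier evaluable patients it can. The statement that one event is insufficient rests on 6 to 12 earlier evaluable patients at the dose and on the denominator as written. If only Expansion patients were counted, one DLT among the first three would reach 33%.

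The patients concerned are 15 evaluable in Stage 1 and at most 41 evaluable (about 45 enrolled) if Stage 2 opens. The documents give no rate for these events. No efficacy endpoint or analysis is affected. This is a cheap improvement of low priority.

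**What to change.** Keep the current Grade 4 sentence in 8.2.7 and add:

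> In Arm B, any Grade 4 toxicity related to durvalumab from first dose through the end of combination dosing (or through the 90-day safety follow-up if combination dosing stops early) will require prompt review by the SRC, which will decide whether to suspend Arm B expansion.

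The sentence requires review only; there is no automatic suspension. Arm A is unaffected, as is single-agent durvalumab after six completed combination cycles. It uses the existing committee and attribution data already collected.

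I would not exempt the Grade 4 events after which Appendix E allows treatment to continue or resume. Such a list would conflict with 10.5, which requires discontinuation after any treatment-related Grade 4 event, and a review-only rule does not need it.

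The cost is an occasional extra SRC teleconference, some of them for expected durvalumab events, and possibly a short Arm B pause if the SRC chooses one. If 1% to 10% of patients have such an event (assumption), the expected number of extra reviews is 15 × 0.01 = 0.15 to 15 × 0.10 = 1.5 in 15 patients, and 45 × 0.01 = 0.45 to 45 × 0.10 = 4.5 in 45.

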8.3 STUDY FLOW AND EXPECTED DURATION OF PATIENT PARTICIPATION

All patients will participate in a Screening Phase, Treatment Phase, and Follow-up Phase.

Screening Phase:

- A 14-day screening period before enrollment (\leq 28 days for baseline biopsy and imaging)
- Patients will be evaluated against study inclusion and exclusion criteria. Patients must meet all inclusion criteria and none of the exclusion criteria at screening in order to be eligible for the study. Assessments required on C1D1 that are performed as part of the screening evaluations and within 72 hours prior to the first dose of study treatment, do not need to be repeated on C1D1.

Treatment Phase:

- Arm A: mRNA-2416 administered for 6 cycles
- Arm B: Combination dosing of mRNA-2416 with durvalumab for 6 cycles. Following completion of 6 cycles of combination dosing, patients may continue with durvalumab as a single-agent until disease progression, unacceptable toxicity, or 24 months of treatment (total), whichever is sooner.

Safety Follow-up:

- Patients will be followed up for safety evaluation 30 and 90 days after their last dose of study treatment.

Disease Progression Follow-up:

Patients who complete study treatment with an overall tumor assessment of stable disease (SD) or better will be followed for tumor assessment 60 and 180 days after their last dose of study treatment, or until disease progression, whichever occurs first.

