9.2 EXCLUSION CRITERIA

Any of the following criteria will exclude patients from study participation:

1. Active central nervous system tumors or metastases
2. Treatment with chemotherapy, radiation (local radiation for palliative care is permitted), hormonal anti-cancer treatment, or biologic therapy < 14 days prior to the first day of study treatment (Cycle 1 Day 1 [C1D1]).
 - b. Treatment with any other investigational agent or treatment with any anti-cancer monoclonal antibody, immunostimulant, or vaccine < 28 days prior to C1D1.
3. Any unresolved toxicity NCI CTCAE Grade ≥ 2 from previous anticancer therapy with the exception of alopecia, vitiligo, and the laboratory values defined in the inclusion criteria

- Patients with Grade ≥ 2 neuropathy will be evaluated on a case-by-case basis after consultation with the Study Physician.
- Patients with irreversible toxicity not reasonably expected to be exacerbated by treatment with durvalumab may be included only after consultation with the Study Physician.

4. History of severe allergic reactions to any of the study drug components
5. Has active or prior documented autoimmune or inflammatory disorders (including inflammatory bowel disease [eg, colitis or Crohn's disease], diverticulitis [with the exception of diverticulosis], systemic lupus erythematosus, Sarcoidosis syndrome, or Wegener syndrome [granulomatosis with polyangiitis, Graves' disease, rheumatoid arthritis, hypophysitis, uveitis, etc]). The following are exceptions to this criterion:
 - Patients with vitiligo or alopecia
 - Patients with hypothyroidism (eg, following Hashimoto syndrome) stable on hormone replacement
 - Patients with any chronic skin condition that does not require systemic therapy
 - Patients without active disease in the last 5 years may be included but only after consultation with the Moderna medical monitor
 - Patients with celiac disease controlled by diet alone.
6. Has a history of primary immunodeficiency, allogenic solid organ transplantation, or tuberculosis.
7. Immunosuppressive doses of systemic steroids or absorbed topical steroids (doses >10 mg prednisone daily equivalent) within 2 weeks before study drug administration
8. Local infection at site of a tumor lesion amenable to injection requiring anti-infective therapy within 2 weeks of the first dose of study drug

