10.13.2 DOSE ESCALATION BIOPSY COLLECTION PLAN

For patients in the dose escalation biopsy cohorts, collection of newly obtained tumor samples during screening and at 1 of the time points as specified below is required unless not medically feasible and agreed by the Sponsor. Up to 9 patients may be enrolled into the Biopsy Cohort Enrichment at each dose level, 3 patients in Group A, 3 in Group B and 3 in Group C.

Escalation Biopsy Group A:

Patients will undergo a baseline biopsy of a lesion distinct from the planned site of intratumoral injection up to 14 days pre-dose Cycle 1 Day 1 and a biopsy within Cycle 1 Day 22 - 28. The primary analysis of the biopsies from biopsy Group A will focus on infiltration of immune effector cells into tumor lesions distal from the tumor lesion(s) that are injected with mRNA-2416 (eg, an abscopal anti-tumor effect).

Escalation Biopsy Group B:

Patients will undergo a baseline tumor biopsy of a lesion that is planned for intratumoral injection up to 14 days pre-dose Cycle 1 Day 1 and a biopsy of the injected tumor lesion 24 to 48 hours post-dose Cycle 1 Day 1. The biopsy site should be the same as, or as close as possible to, the site of injection of mRNA-2416.

Escalation Biopsy Group C:

Patients will undergo a baseline tumor biopsy of a lesion that is planned for intratumoral injection up to 14 days pre-dose Cycle 1 Day 1 and a biopsy of the injected tumor lesion 24 to 48 hours post-dose Cycle 2 Day 1. The biopsy site should be the same as, or as close as possible to, the site of injection of mRNA-2416.

The primary analysis of the biopsies from biopsy Groups B and C will focus on expression of OX40L protein immediately after injection of mRNA.

Table 7: Dose Escalation Tumor Biopsy Analyses by Group

Group	Biopsy Timing	Biopsy Site	Analyses	
			OX40/OX40L Expression	Additional Tumor Microenvironment Characterization by IHC/ QIF and/or RNAseq
A	First biopsy: Within 14 days pre-study (C1D1)	Any lesion NOT planned for injection of study drug	X	X
	Second biopsy: Between Cycle 1 Day 22-28	Lesion that has NOT been injected with study drug (same lesion as baseline)	X	X
B	First biopsy: Within 14 days pre-study (C1D1)	Any lesion planned for injection of study drug	X	X
	Second biopsy: 24-48 hrs after C1D1 injection	Lesion injected with study drug *biopsy should be at the injection site if possible (same lesion as baseline)	X	X

Group	Biopsy Timing	Biopsy Site	Analyses	

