10.13.3 DOSE EXPANSION BIOPSY COLLECTION PLAN

For all patients in dose expansion, collection of newly obtained tumor samples during screening and at 1 of the time points as specified below is required unless not medically feasible and agreed by the Sponsor. An additional optional biopsy at the time of treatment response or disease progression is also requested if medically feasible.

For all patients in dose expansion, biopsies at screening should be performed on a lesion which is planned for injection of study treatment, as well as a distal non-visceral lesion which is not planned for injection of study treatment if medically feasible. Similarly, the on-treatment biopsies should be performed on a lesion which has been injected with study treatment, as well as on a distal non-visceral lesion which has not been injected with study treatment if medically feasible. Every attempt should be made to biopsy the same injected and distal lesions at all time points.

Patients in dose expansion will be assigned to biopsy groups which each have a different timepoint for the on-treatment biopsies, as specified below.

Arm A Expansion Biopsy Group D:

Within 14 days pre-dose Cycle 1 Day 1: A baseline tumor biopsy of a lesion that is planned for intratumoral injection, as well as a distal non-visceral lesion which is not planned for injection if medically feasible.

24 to 48 hours post-dose Cycle 1 Day 1: Tumor biopsy of the injected tumor lesion, as well as a distal non-visceral lesion which has not been injected with study treatment if medically feasible. The biopsy of the injected lesion should include or be as close as possible to the injection site.

Arm A Expansion Biopsy Group E:

Within 14 days pre-dose Cycle 1 Day 1: A baseline tumor biopsy of a lesion that is planned for intratumoral injection, as well as a distal non-visceral lesion which is not planned for injection if medically feasible

Pre-dose Cycle 2 Day 1: Tumor biopsy of the injected tumor lesion, as well as a distal non-visceral lesion which has not been injected with study treatment if medically feasible. The biopsy of the injected lesion should include or be as close as possible to the injection site.

Arm B Expansion Biopsy Group F:

Within 14 days pre-dose Cycle 1 Day 1: A baseline tumor biopsy of a lesion that is planned for intratumoral injection, as well as a distal non-visceral lesion which is not planned for injection if medically feasible.

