24 to 48 hours post-dose Cycle 1 Day 1: Tumor biopsy of the injected tumor lesion, as well as a distal non-visceral lesion which has not been injected with study treatment if medically feasible. The biopsy of the injected lesion should include or be as close as possible to the injection site.

Arm B Expansion Biopsy Group G:

Within 14 days pre-dose Cycle 1 Day 1: A baseline tumor biopsy of a lesion that is planned for intratumoral injection, as well as a distal non-visceral lesion which is not planned for injection if medically feasible

Pre-dose C1D15: Tumor biopsy of the injected tumor lesion, as well as a distal non-visceral lesion which has not been injected with study treatment if medically feasible. The biopsy of the injected lesion should include or be as close as possible to the injection site.

Arm B Expansion Biopsy Group H:

Within 14 days pre-dose Cycle 1 Day 1: A baseline tumor biopsy of a lesion that is planned for intratumoral injection, as well as a distal non-visceral lesion which is not planned for injection if medically feasible

Pre-dose Cycle 2 Day 1: Tumor biopsy of the injected tumor lesion, as well as a distal non-visceral lesion which has not been injected with study treatment if medically feasible. The biopsy of the injected lesion should include or be as close as possible to the injection site.

Table 8: Arm A Dose Expansion Tumor Biopsy Analyses by Group

Group	Biopsy Timing	Biopsy Sites	Analyses	
			OX40/OX40L Expression	Additional Tumor Microenvironment Characterization by IHC/ QIF and/or RNAseq
D	First biopsies: Within 14 days pre-study (C1D1)	1) Lesion planned for injection of study drug 2) Lesion NOT planned for injection of study drug	X	X
	Second biopsies: 24-48 hrs after C1D1 injection	1) Lesion injected with study drug 2) Lesion NOT injected with study drug	X	X
E	First biopsies: Within 14 days pre-study (C1D1)	1) Lesion planned for injection of study drug 2) Lesion NOT planned for injection of study drug	X	X
	Second biopsies: Pre-dose C2D1 injection	1) Lesion injected with study drug 2) Lesion NOT injected with study drug	X	X

OX40L=OX40 ligand; QIF= quantitative immunofluorescence; RNAseq= RNA sequencing

Table 9: Arm B Dose Expansion Tumor Biopsy Analyses by Group

Group	Biopsy Timing	Biopsy Sites	Analyses	
			OX40/OX40L Expression	Additional Tumor Microenvironment Characterization by IHC/ QIF and/or RNAseq

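### Protocol 8.3 allows the baseline tumor biopsy up to 28 days before enrollment, while 10.13 requires it within 14 days before C1D1 dosing; the wider window can place baseline tissue before the last dose of prior therapy

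*Protocol*

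**What the plan says.** **Timing of the baseline biopsy.**

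- Protocol 8.3 describes "A 14-day screening period before enrollment" and adds, in parentheses, an allowance of up to "28 days for baseline biopsy and imaging".
- Protocol 10.13.2 (Escalation Groups A to C) places the baseline biopsy "up to 14 days pre-dose Cycle 1 Day 1".
- Protocol 10.13.3 (Expansion Groups D to H) uses the same limit: "Within 14 days pre-dose Cycle 1 Day 1: A baseline tumor biopsy of a lesion that is planned for intratumoral injection". Tables 7, 8 and 9 repeat 14 days for every group.
- The Schedule of Events (Protocol Section 3) marks the biopsy in the screening column, Day -14 to Day -1. For detail it refers to Section 10.5, which covers dose omissions and discontinuation. The biopsy plan is in 10.13.

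The 28-day allowance causes no conflict for imaging, because 10.10 also gives 28 days before C1D1. No section says which biopsy window governs. The waiver in 10.13.2 and 10.13.3, for medical infeasibility with sponsor agreement, excuses collection and does not widen the window.

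**Washout.** Exclusion 2 (Protocol 9.2) bars chemotherapy, radiation, "hormonal anti-cancer treatment, or biologic therapy < 14 days prior to the first day of study treatment". It exempts palliative local radiation. A sub-item sets a longer limit for investigational agents, anti-cancer monoclonal antibodies and others: "immunostimulant, or vaccine < 28 days prior to C1D1".

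**Analysis.** SAP Section 4 defines baseline as the last assessment before the first dose, with no limit on its age. SAP Section 10 allows descriptive change-from-baseline summaries of the biopsy markers. These serve the exploratory endpoints in Protocol 7.6.

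**The concern.** A mandatory invasive procedure has two windows with two different anchors. The wider one reads like a deliberate exception to the 14-day screening period, and its imaging half is right, so a site has no cue that the biopsy half conflicts with 10.13. A site that follows the Schedule of Events reference to 10.5 does not reach the 14-day rule.

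The difference between the windows matters for interpretation because it falls where the 14-day washout has not yet begun. Tissue taken on Day -28 to Day -15 may come from a patient still receiving earlier treatment. The paired comparison would then mix the effect of stopping that treatment with the effect of study drug, and there is no concurrent untreated group to separate them. Operationally, the same sample complies with one section and deviates from another, which could produce a recorded deviation or a request to repeat the biopsy.

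**Working it through.** The plan states no figure to reproduce here. The check counts days before C1D1 against each rule.

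**Inputs.** Biopsy window in 8.3: at most 28 days before enrollment. Biopsy window in 10.13: at most 14 days before the C1D1 dose. Therapy with the shorter washout is excluded if given fewer than 14 days before C1D1, so Day -14 and earlier are allowed. Agents with the longer washout are excluded if given fewer than 28 days before C1D1, so Day -28 and earlier are allowed.

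**Assumption.** Enrollment falls on C1D1. The case where it does not is shown in step 4.

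**Step 1: days on which the sections disagree.** 8.3 admits Days -28 to -1 (28 days). 10.13 admits Days -14 to -1 (14 days). The discordant days are -28 to -15: 28 - 14 = 14 days.

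**Step 2: days on which a biopsy is in window and prior therapy is still permitted.**

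| Prior therapy | Under 8.3 | Under 10.13 |
|---|---|---|
| Chemotherapy, non-palliative radiation, hormonal, biologic (14-day washout) | Days -28 to -14 (15 days) | Day -14 only |
| Investigational agent, anti-cancer antibody, immunostimulant, vaccine (28-day washout) | Day -28 only | none |
| Palliative local radiation (exempt) | any day | any day |

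All 14 discordant days fall in the first row's overlap under 8.3.

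**Step 3: longest interval between the paired biopsies.** This is the oldest permitted baseline plus the latest planned on-treatment time after the C1D1 dose, ignoring visit windows.

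| Groups | On-treatment biopsy, latest day after C1D1 dose | Using 8.3 | Using 10.13 |
|---|---|---|---|
| B, D, F (24 to 48 h after C1D1) | 2 | 28 + 2 = 30 | 14 + 2 = 16 |
| G (pre-dose C1D15) | 14 | 28 + 14 = 42 | 14 + 14 = 28 |
| A (C1 Day 22 to 28) | 27 | 28 + 27 = 55 | 14 + 27 = 41 |
| E, H (pre-dose C2D1) | 28 | 28 + 28 = 56 | 14 + 28 = 42 |
| C (24 to 48 h after C2D1) | 30 | 28 + 30 = 58 | 14 + 30 = 44 |

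The absolute difference is 14 days throughout. It nearly doubles the interval only in Groups B, D and F.

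**Step 4: effect of the anchor.** If dosing follows enrollment by k days, 8.3 admits biopsies back to Day -(28 + k). The discordant days become 14 + k, and the overlap with 28-day-washout agents becomes 1 + k days. The figures above are the case k = 0.

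**The case against.** The strongest case against is that this is one parenthesis in a study-flow summary. Sections 10.13.2 and 10.13.3, three tables and the Schedule of Events column all agree on 14 days. The affected endpoints are exploratory, the SAP summaries are descriptive and optional, and the biomarker results go to a separate report. Collection can be waived or omitted by the sponsor, so a repeat biopsy is possible but not established. All of that stands, and it keeps the point small. It does not settle which window a site should follow, because no section gives 10.13 precedence.

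A reader might also infer more than the documents support:

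- **That a biopsy within 14 days is always clear of prior therapy.** It is not. Exclusion 2 still allows treatment on Day -14, and palliative local radiation on any day.
- **That the 14-day window removes carry-over from earlier treatment.** Chemotherapy on Day -14 with a biopsy on Day -13 complies with both rules. Recent exposure follows from the washout length as well as from the biopsy window.
- **That prior checkpoint antibodies are part of the overlap.** As anti-cancer antibodies they carry the 28-day washout, so under 8.3 they meet the biopsy window only at the Day -28 boundary when k = 0.

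Overlap can already be traced by hand, because start and stop dates of previous regimens are collected (Schedule of Events, footnote 2) and prior therapies are listed (SAP 6.3.2). Nothing in the plan, however, joins those dates to the biopsy date.

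**Conclusion.** The inconsistency is real and in the current text. With enrollment on C1D1, 14 of the 28 days that 8.3 permits breach 10.13, and on each of them an eligible patient may still be on treatment covered by the 14-day washout. Under 10.13 that overlap is a single day. The paired-biopsy interval can reach about 30 days instead of about 16 in Groups B, D and F; elsewhere several weeks are already planned. Because the SAP baseline has no window, a Day -28 to Day -15 sample would be analysed as baseline without a mark.

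The consequence is confined to the exploratory tissue comparisons and to deviation handling. A reader might infer a threat to the Phase II response rate or to the two-stage sample sizes. Neither uses the biopsy, and baseline imaging has a consistent 28-day window. The documents do not show how many biopsies, if any, fell in the discordant days. This is a low-priority correction.

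**What to change.** 1. Reconcile 8.3 with 10.13.2, 10.13.3 and Tables 7 to 9 so that one baseline biopsy window applies, counted from one anchor (enrollment or the C1D1 dose). Which window to keep is for the sponsor to decide.
2. Correct the Schedule of Events reference for tumor biopsy from Section 10.5 to 10.13.
3. In the biomarker listings and summaries, flag any baseline biopsy taken on or before the last dose of prior anti-cancer therapy. The flag identifies overlap only; it does not catch tissue taken shortly after a last dose. With 3 patients per escalation biopsy group at each dose level, dropping flagged patients would leave at most two, so a flag is more useful there than a re-analysis.

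The cost is a phrase and a cross-reference in the next amendment, plus one derived variable. The variable uses the prior-therapy dates and the sample collection log that the eCRF already holds. No added biopsy, visit or data item is needed.
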